4.9. Framework

Two conceptual frameworks influenced the design of this study. First, the health belief model summarizes how and why people make health behaviour choices (33) and includes the constructs of perceived: susceptibility, severity, benefit, and barriers—many of which can be targeted by SMES. Second, the framework proposed by Campbell et al postulates how financial barriers may affect clinical outcomes. These frameworks were used to inform the development of the interventions.

The overarching purposes of the interventions in the ACCESS study will be to:

(1) Increase initiation and adherence to medications that have been proven to reduce the risk of cardiovascular events in this population of high-risk patients, including HMG-CoA reductase inhibitors (Statins) (34) and renin-angiotensin-aldosterone system inhibitors (ACE inhibitors [ACEi] and angiotensin receptor blockers [ARBs]) (35).

(2) Encourage participants to make positive health behavior changes, including healthy dietary choices, engagement in physical activity, cessation of tobacco use, and increased adherence to all preventive medications.

4.10. Interim Analyses and Stopping Guidance

The trial interventions were deemed low risk to cause adverse events, so no DSMB or interim analyses were planned, or were possible given the use of administrative data to assess outcomes.

4.11. Timing of Final Analysis

The final analysis will be started in the summer of 2021, which will focus on the cleaning and preparation of the self-reported outcome data which were collected through the survey data.

We anticipate receipt of the administrative data from Alberta Health in early 2022, with data cleaning to follow and the final analysis to begin March 1, 2022, to be completed by July 1, 2022.

4.12. Timing of Other Analysis

Secondary analyses will be completed through the summer and fall of 2022, with further sub-analyses to be conducted thereafter.

4.13. Trial Comparisons

The impact of the two interventions will be conducted independently of one another. We will compare each intervention arm to those who did not receive that specific intervention.

5. Statistical Principles

5.1. Confidence Intervals and P-values

In all our analyses, we will calculate 95% Confidence intervals around all point estimates and will calculate p-values using appropriate statistical tests. We will consider our alpha value to be 0.05.

5.2. Adjustments for Multiplicity

For the secondary outcomes that are the individual components of the primary outcome, we will adjust for multiplicity using the Benjamini-Hochberg procedure (36). We will initially sort the primary outcome individual component secondary outcomes by p-value. Ranks will be assigned in ascending order of p-value. The Benjamini-Hochberg critical value will be calculated using the formula $(i/m)Q$, where:

- i = the individual outcome's p-value's rank,
- m = total number of tests,
- Q = the false discovery rate (25%).

We will then compare our original p-values to the critical value calculated. The largest p-value that is smaller than the critical value will be the last individual outcome that is considered statistically significant.

Given that the other secondary outcomes are exploratory, we will not make adjustments for multiplicity in these analyses (37).

6. Outcome Definitions

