4.3. Primary Outcomes

Outcomes of relevance to patients with chronic disease: When management of chronic disease is suboptimal for extended periods, patients may be hospitalized for complications (25). While myocardial infarction, stroke, and the need for revascularization are the classical complications (and are components of our primary outcome), hospitalization for chronic disease-related ambulatory care sensitive conditions are also relevant, since these complications can serve as a proxy for poor control of chronic disease. Ambulatory care sensitive conditions (ACSC) are those for which “timely and effective outpatient care, including use of appropriate medications, can help to reduce the risk of hospitalization by preventing the onset of an illness or condition, or managing a chronic disease” (26). While several agencies have examined what constitutes an ACSC for the chronic diseases under study, the most applicable definition of ACSC for cardiovascular diseases, diabetes and hypertension using a Canadian context is from CIHI (2009). Since this does not include hospitalizations for CKD-related ACSC, this list was taken from a recent Canadian study (27). Importantly, these potentially preventable hospitalizations are clinically relevant to patients and represent an important economic burden for the system (28), which might be avoided through interventions which optimize patient management (29,30).

Primary Outcome: The primary outcome is the composite rate of any of the following: all-cause mortality, myocardial infarction, stroke, coronary revascularization (coronary artery bypass grafting, angioplasty, or coronary stenting), and hospitalizations for chronic disease-related ambulatory care sensitive conditions. Given that an individual may have

multiple events during the follow-up period, we have chosen to use a rate outcome rather than a simple binary composite outcome.

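### With five components, Benjamini-Hochberg at a 25% false discovery rate is never stricter than no adjustment, and is looser from the second rank on

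*Combined protocol and SAP*

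**What the plan says.** All references are to the combined protocol and SAP unless noted.

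- Section 4.4 makes each component of the primary outcome a secondary outcome. Section 4.3 names the components: "all-cause mortality, myocardial infarction, stroke, coronary revascularization" "and hospitalizations for chronic disease-related ambulatory care sensitive conditions". That is five.
- Section 5.2 says of these components: "we will adjust for multiplicity using the Benjamini-Hochberg procedure". The critical value is (i/m)Q, where i is the rank of the p-value, "m = total number of tests", and "Q = the false discovery rate (25" percent).
- The decision rule is the usual step-up: "The largest p-value that is smaller than the critical value will be the last individual outcome that is considered statistically significant".
- Section 5.1 sets the general level: "We will consider our alpha value to be 0.05". It also promises 95% confidence intervals around all point estimates.
- Section 5.2 calls the other secondary outcomes exploratory and leaves them unadjusted.
- Section 4.13 says the two interventions are assessed independently of one another.

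No value of m is given, no thresholds are printed, and no reason is offered for 25%.

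**The concern.** A multiplicity adjustment exists to make it harder to call a result significant when several are tested. With five tests and Q = 0.25, the smallest threshold is 0.25/5 = 0.05, the level each component would face with no adjustment, and every later threshold is higher. The procedure therefore protects against nothing that an unadjusted 5% test would let through, and it admits results that such a test would reject.

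Two consequences follow inside the plan. The components, including death, myocardial infarction and stroke, face a looser standard than the outcomes the plan itself calls exploratory, which are judged at 0.05. A component could also be reported as significant after adjustment while its 95% confidence interval includes no effect. Component results are easily quoted on their own, and the label would suggest more protection than was applied.

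**Working it through.** The plan prints no thresholds, so there is no figure of its own to reproduce on this point. Inputs: Q = 0.25 and the formula (section 5.2), five components (section 4.3), separate analysis of each intervention (section 4.13), alpha 0.05 (section 5.1).

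**Thresholds at m = 5.** (i/5) × 0.25 = 0.05i:

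| Rank i | Q = 0.25 (plan) | No adjustment | Q = 0.05 |
|---|---|---|---|
| 1 | 0.05 | 0.05 | 0.01 |
| 2 | 0.10 | 0.05 | 0.02 |
| 3 | 0.15 | 0.05 | 0.03 |
| 4 | 0.20 | 0.05 | 0.04 |
| 5 | 0.25 | 0.05 | 0.05 |

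**It can only add findings.** Suppose k of the five p-values are below 0.05. The k-th smallest is then below 0.05, which is at most 0.05k, its threshold. So all k are declared significant. This needs no assumption about effects or correlation.

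**What it can add.** If the two smallest p-values are 0.06 and 0.08 and the rest exceed 0.25, the first fails its own threshold (0.06 > 0.05) but the second passes (0.08 < 0.10), so both are declared significant although neither is below 0.05. A component at p = 0.24 is declared significant if all five p-values are below 0.25.

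**Error rates at m = 5.** Assumptions: independent tests, and 80% power at 0.05 for each component with a true effect. Unadjusted figures follow from 1 − 0.95^5 = 22.6% and 1 − 0.95^4 = 18.5%; the others come from simulation of 400,000 sets.

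| True effects | Chance of any false claim, Q = 0.25 | Unadjusted 0.05 | Q = 0.05 |
|---|---|---|---|
| 0 of 5 | 25% | 22.6% | 5% |
| 1 of 5 | 34% | 18.5% | 6.6% |
| 4 of 5 (one null left) | 24% | 5% | about 4% |

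The plan's rule removed an unadjusted finding in none of the simulated sets. It added at least one component with p of 0.05 or more in 7% of sets with no true effects and in 54% with four.

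**Correlated components.** With an assumed correlation of 0.5, the chance of any false claim is 21% against 18% unadjusted (no true effects) and 28% against 16% (one true effect).

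**On the false discovery rate itself.** With one true effect and independent tests, the rate under the plan is (4/5) × 0.25 = 20%, against 11% with no adjustment (simulation).

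**Other readings of m.** Section 6.1 defines ambulatory care sensitive hospitalization in five rows (diabetes, kidney disease, hypertension, heart failure, coronary disease). Testing each gives m = 4 + 5 = 9; pooling both interventions gives m = 10 or 18.

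| m | First thresholds | Ranks below 0.05 | Any false claim, no true effects: plan v unadjusted |
|---|---|---|---|
| 9 | 0.028, 0.056 | 1 of 9 | 25% v 37% |
| 10 | 0.025, 0.05, 0.075 | 1 of 10 | 25% v 40% |
| 18 | 0.014, 0.028, 0.042, 0.056 | 3 of 18 | 25% v 60% |

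With two true effects the plan's rule is looser again: about 43% v 30% at m = 9 and 44% v 34% at m = 10.

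**The case against.** **25% is a false discovery rate, not an alpha.** This is right. Benjamini-Hochberg does control that rate at 25%, and a specific rule for one family may stand beside a general alpha. The procedure is not misapplied, and section 5.2 does not strictly conflict with section 5.1. But the section is presented as an adjustment and its output is the label of statistical significance, and with five tests that label is never harder to earn than with no adjustment. The comparison also goes the same way on the procedure's own metric (20% v 11%).

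**m is not fixed.** This also stands. At m = 9 or 10 a lone p of 0.03 would be removed, and with no true effects the rule is then a real adjustment. With one true effect at m = 10 the two approaches are about equal (36% v 37%). The statement that the rule never removes a finding is therefore confined to m = 5. Sections 4.3 and 4.13 favour that reading, and leaving m open is itself a gap.

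**Only secondary results are affected, and the analysis may be finished.** The primary composite, its model and the sample size are untouched, and the promised 95% intervals let a reader see when a component includes no effect. Section 4.11 schedules completion by July 1, 2022, and the introduction of the separate secondary-analysis SAP already describes main findings; that SAP does not use this rule. A change to Q now would be post hoc. That alters how the correction is made, not whether the rule works as an adjustment.

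**Conclusion.** The concern holds. On the natural reading of five components per intervention, the stated adjustment is equal to an unadjusted 5% test at the first rank and looser at every other rank. This is arithmetic and rests only on m = 5. The size of the excess error depends on assumptions: under independence and 80% power it runs from slight with no true effects (25% v 22.6%) to roughly fivefold for the last null component when four are truly affected (24% v 5%). The direction is unchanged at a correlation of 0.5. Under larger families the rule tightens the lowest one to three ranks but still accepts p-values up to 0.25 at the highest. The section should not stand as written, because it cannot support a statement that component results were protected against multiplicity.

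**What to change.** In section 5.2, state that m = 5 within each intervention, with ambulatory care sensitive hospitalization counted as one component, and set Q = 0.05. The thresholds become 0.01, 0.02, 0.03, 0.04 and 0.05. Q = 0.10 would still exceed 0.05 from the third rank (0.06, 0.08, 0.10). If the sponsor wants to keep a larger Q, the plan should justify it and should not describe the result as an adjustment that protects component claims; presenting the components as descriptive, with unadjusted intervals, would be more candid.

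If the components have already been analysed, report the unadjusted p-values and 95% intervals, state the Q and m used, show the Q = 0.05 result beside them, and label the change as made after the analysis.

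The cost is two short edits and no new data. Fewer components will be called significant: a component with 80% power at 0.05 (standardized effect 1.96 + 0.84 = 2.80) has power of about Φ(2.80 − 2.58) = 59% at 0.01, the threshold it faces when no other component helps it through.

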6.1. Primary outcome

Record of any of the following identified within the Discharge Abstract Database will be counted as one primary outcome. The number of composite outcomes will be used; therefore, any one individual may have multiple outcomes within the observation window.

The rates of the composite outcome will be calculated by generating the observation time, defined as the period from randomization to study completion, taking into consideration censoring for death or outmigration.

Outcome	Description	Classification Source	Codes included	Exclusions	Source
Myocardial Infarction	Acute myocardial infarction Subsequent myocardial infarction	ICD-10	I21.X I22.X	None	Quan et al. (38), Austin et al. (39)
Stroke	Central retina artery occlusion Cerebral infarction Stroke, not specified as hemorrhage or infarction Intracerebral hemorrhage Subarachnoid hemorrhage Transient cerebral ischemic attacks	ICD-10	H34.1 I63.X I64.X I61.X I60.X G45.X	None	Kokotailo and Hill (40)
Coronary Revascularization	Coronary Angioplasty Coronary endarterectomy/excision Coronary local pharmacotherapy	Canadian Classification of Health Interventions (CCI)	1.IJ.50 1.IJ.57 1.IL.35 1.IJ.76		CIHI

	Coronary Artery Bypass				
Death	Death (all-cause)	Vital Statistics			
Ambulatory Care-Sensitive Hospitalization for Diabetes	Type 1 DM with coma Type 1 DM with acidosis Type 1 DM with hypoglycaemia Type 1 DM without (mention of) complication Type 2 DM with coma Type 2 DM with acidosis Type 2 DM with hypoglycaemia Type 2 DM without (mention of) complications Other specified DM with coma Other specified DM with acidosis Other specified DM with hypoglycaemia Other specified DM without (mention of) complication Unspecified DM with coma Unspecified DM with acidosis Unspecified DM with hypoglycaemia Unspecified DM without (mention of) complication	ICD-10	E10.0^^ E10.1^^ E10.63 E10.9^^ E11.0^^ E11.1^^ E11.63 E11.9^^ E13.0^^ E13.1^^ E13.63 E13.9^^ E14.0^^ E14.1^^ E14.63 E14.9^^	None	CIHI

Outcome	Description	Classification Source	Codes included	Exclusions	Source
Ambulatory Care-Sensitive	Type 2 diabetes mellitus with ketoacidosis		E11.10 E10.10	None	Gao et al. (41)

Hospitalization for Chronic Kidney Disease	Type 1 diabetes mellitus with ketoacidosis Type 2 diabetes mellitus with ketoacidosis with lactic acidosis Type 1 diabetes mellitus with ketoacidosis with lactic acidosis Type 2 diabetes mellitus with coma Type 1 diabetes mellitus with coma Hyperosmolality and hypernatremia Hyperkalemia Fluid overload Malignant hypertension Heart failure Hypertensive heart disease Hypertensive heart and renal disease Hypertensive heart and renal disease Ischaemic cardiomyopathy Dilated cardiomyopathy Other restrictive cardiomyopathy Alcoholic cardiomyopathy Cardiomyopathy due to drugs and other external agents Other cardiomyopathies Cardiomyopathy, unspecified	ICD-10	E11.12 E10.12 E11.00 E10.00 E87.0 E87.5 E87.7 I10.1 I50.x I11.0 I13.0 I13.2 I25.5 I42.0 I42.5 I42.6 I42.7 I42.8 I42.9		
Ambulatory Care-Sensitive Hospitalization for Hypertension	Benign hypertension Malignant hypertension Hypertensive heart disease		I10.0 I10.1 I11	See below	CIHI
Outcome	Description	Classification Source	Codes included	Exclusions	Source
			I109.9	None	

Ambulatory Care-Sensitive Hospitalization for Heart Failure	Rheumatic heart disease, unspecified Hypertensive Heart Disease Hypertensive Heart and Renal Disease and stage 1 through stage 4 chronic kidney disease, or unspecified chronic kidney disease Hypertensive heart and chronic kidney disease without heart failure, with stage 1 through stage 4 chronic kidney disease, or unspecified chronic kidney disease Hypertensive Heart And Renal Disease and with stage 5 chronic kidney disease, or end stage renal disease		I11.0 I13.0 I13.10 I13.2		CIHI
Ambulatory Care-Sensitive Hospitalization for Coronary artery disease	Angina pectoris Other current complications following acute myocardial infarction Acute coronary thrombosis not resulting in myocardial infarction Other forms of acute ischemic heart disease Acute ischemic heart disease, unspecified		I20 I23.82 I24.0 I24.8 I24.9	See below	CIHI

* Excludes hospitalizations with one of the following cardiac procedure codes:

CCP: 47^^, 480^–483^, 489.1, 489.9, 492^–495^, 497^, 498^

ICD-9-CM: 336, 35^^, 36^^, 373^, 375^, 377^, 378^, 379.4–379.8

CCI: 1HA58, 1HA80, 1HA87, 1HB53, 1HB54, 1HB55, 1HB87, 1HD53, 1HD54, 1HD55, 1HH59, 1HH71, 1HJ76, 1HJ82, 1HM57, 1HM78, 1HM80, 1HN71, 1HN80, 1HN87, 1HP76, 1HP78, 1HP80, 1HP82, 1HP83, 1HP87, 1HR71, 1HR80, 1HR84, 1HR87, 1HS80, 1HS90, 1HT80, 1HT89, 1HT90, 1HU80, 1HU90, 1HV80, 1HV90, 1HW78, 1HW79, 1HX71, 1HX78, 1HX79, 1HX80, 1HX83, 1HX86, 1HX87, 1HY85, 1HZ53 rubric (except 1HZ53LAKP), 1HZ55 rubric (except 1HZ55LAKP), 1HZ56, 1HZ57, 1HZ59, 1HZ80, 1HZ85, 1HZ87, 1IF83, 1IJ50, 1IJ55, 1IJ57, 1IJ76, 1IJ86, 1IJ80, 1IK57, 1IK80, 1IK87, 1IN84, 1LA84, 1LC84, 1LD84, 1YY54LANJ

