4.6. Timing of outcomes as assessments

The primary outcome data was ascertained through administrative health data held within the province of Alberta, including linked datasets such as: laboratory data, pharmacy dispensation data, acute care data, outpatient physician claims data, and demographic data. Participants were followed for a minimum of 2.5 years from the time of randomization through until March 30, 2021. This data will be available as of early 2022.

Self-reported outcome measures were obtained via electronic and paper-based surveys which were sent to participants 6-, 18-, and 33-months after randomization.

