7.2. Baseline Characteristics

Baseline characteristics will be reported in a Table using descriptive summary statistics. These will be stratified by group assignment, and t-tests/Chi2 tests will be used to examine for inter-group differences in these characteristics.

8. Data Sources

The main data source for the trial will be the ACCESS trial RedCAP database. This contains participant group assignments and all patient reported measures from baseline, 6-month, 18-month, and 33-month surveys. It also contains individuals' unique provincial health number which will permit deterministic linkage to administrative health databases held by Alberta Health (including Alberta Precision Laboratory data, Pharmacy Information Network Data, Practitioner Claims data, Discharge Abstract Database, National Ambulatory Care Reporting System data). All PHNs were verified at the time of study enrollment to be sure that they were accurate and active. In cases where a deterministic linkage is not possible, probabilistic linkage using name, date of birth, and postal code will be used.

9. Interventions (s)

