10.9. Sensitivity Analyses

Sensitivity analyses will be conducted as follows:

- Excluding those who have admissions/costs in the top 1% of all participants
- Excluding participants who resided in the same household as another participant.
- We will also conduct a complete case analysis to examine the effects of the missing data, where relevant (ie. Self-reported outcomes).

11. Interaction between intervention arms

Given the factorial design of the trial, we will assess for multiplicative interaction. Because each of our two interventions was designed to address very different patient barriers to

medication adherence (financial barriers vs. Knowledge/motivation), we don't anticipate major multiplicative interaction effects.

12. Health Economic Analysis

The primary outcome will be mean total 3-year in-study health care costs for patients receiving copayment elimination (or not) and those receiving MOXIE (or not), adjusting for co-intervention received. We will include costs for hospitalization and ED visits, physician claims (specialist and primary care physician visit and procedure billing costs), prescription medications (including those subject and not subject to copayment elimination), nonphysician ambulatory costs (day medicine and day surgery clinics), and outpatient diagnostic imaging and laboratory costs. The total costs will be calculated as the sum of these costs. Alberta Health uses Canadian Institute of Health Information case-mix grouper methods to estimate hospital costs and ambulatory-case costing methods to estimate outpatient costs.

Physician claims will be based on the amount paid by Alberta Health. The cost of medications will be estimated by combining a database containing a comprehensive list of medications dispensed to all Alberta residents with a price list from Alberta Blue Cross, including dispensing fee. Diagnostic imaging and laboratory costs will be based on estimates provided by Alberta Health Services. All costs will be reported in 2021 Canadian dollars.

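### Coronary revascularization counts as a primary event in any setting, but section 6.1 finds it only through the Discharge Abstract Database; if day-case procedures leave no discharge abstract, they score no event

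*Combined protocol and SAP*

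**What the plan says.** All references are to the combined protocol and SAP unless noted.

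- **Section 4.3** includes in the primary composite "coronary revascularization (coronary artery bypass grafting, angioplasty, or coronary stenting), and hospitalizations for chronic disease-related ambulatory care sensitive conditions". Within this phrase, hospitalization belongs to the ambulatory-care-sensitive component. Revascularization is named by procedure, not by setting.
- **Section 6.1** gives the operational rule: "Record of any of the following identified within the Discharge Abstract Database will be counted as one primary outcome". The table below it assigns death to "Vital Statistics". The revascularization row gives Canadian Classification of Health Interventions (CCI) codes 1.IJ.50, 1.IJ.57, 1.IL.35 and 1.IJ.76, and CIHI as the source of the code list. It names no second database in which to look for them.
- **Section 8** lists among the databases for linkage "Practitioner Claims data, Discharge Abstract Database, National Ambulatory Care Reporting System data".
- **Section 4.6** says that primary-outcome data come from linked datasets such as "laboratory data, pharmacy dispensation data, acute care data, outpatient physician claims data, and demographic data". It assigns none of these to a particular component and does not name NACRS.
- **Section 12** costs "nonphysician ambulatory costs (day medicine and day surgery clinics") under their own heading, apart from hospitalization.
- **Section 4.4** makes each component of the primary endpoint a secondary outcome. **Section 5.2** tests the components under the Benjamini-Hochberg procedure.

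**The concern.** The outcome is defined by procedure and ascertained by setting. Suppose two participants have the same elective stent. One stays overnight and has a discharge abstract; the other goes home the same day. Under section 6.1 the first scores an event. The second scores nothing if a same-day procedure is recorded only in the ambulatory database. Whether the event counts would then depend on local admission practice.

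Two results are exposed. The primary composite loses events and therefore some precision. The revascularization component, reported and tested separately, loses its whole day-case share, so its absolute rate is too low.

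**Working it through.** **Step 1. Does the text leave the gap?**

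| Question | Where | Answer |
|---|---|---|
| Must the revascularization be inpatient? | 4.3 | No such condition |
| Where is it looked for? | 6.1 | Discharge Abstract Database (DAD) |
| Is another source named for it? | 6.1 table | No; only death has one |
| Is an ambulatory database listed for linkage? | 8 | Yes, NACRS |
| Does any outcome definition use NACRS? | 6.1 to 6.3 | No |
| Is day surgery treated as hospitalization? | 12 | No, as ambulatory care |

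The documents do not say that DAD lacks day procedures. That is inferred from the database names and from the split in section 12.

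**Step 2. Would another component recover the event?** No. The ambulatory-care-sensitive components are hospitalizations. For hypertension and coronary artery disease the table also refers to a footnote: "Excludes hospitalizations with one of the following cardiac procedure codes". Its list includes 1IJ50, 1IJ57 and 1IJ76. A procedure done during an infarction admission has an infarction record in DAD that scores anyway. A stand-alone day-case procedure has no such backup.

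**Step 3. Reproduce the planned sample size.** Inputs from section 4.8: rate 0.14 per year, rate ratio 0.88, 3 years, 80% power, 1:1 allocation, alpha 5% (taken as two-sided). The Signorini formula for Poisson regression with a 1:1 binary covariate is

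N = [z(0.975)·√4 + z(0.80)·√(2 + 2/0.88)]² / [3 × 0.14 × (ln 0.88)²]

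= [1.960 × 2 + 0.8416 × 2.0671]² / [0.42 × 0.016341]

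= 32.031 / 0.0068634 = 4666.97, rounded up to **4667**.

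The 1% allowance gives 4667 × 1.01 = 4713.7, or **4714**. Both stated figures are reproduced, so the plan's arithmetic is sound.

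**Step 4. Effect of missing a share f of composite events.** The documents give neither the revascularization share of events nor the day-case share. Assume the first is 10% to 20% and the second 15% to 40%:

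f = 0.10 × 0.15 = 1.5% up to f = 0.20 × 0.40 = 8%.

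Both ranges are assumptions, and the true value could lie below them. Planned events in a two-group comparison are (4667/2) × 3 × 0.14 × (1 + 0.88) = 1843, so this is about 28 to 147 events.

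Power at N = 4667, with the rate ratio kept at 0.88, is

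Φ{ [√(N × 3 × rate × (ln 0.88)²) − 1.960 × 2] / √(2 + 2/0.88) }.

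*Case A: 14 per 100 counted events in all settings.* The DAD-only rate is 14 × (1 − f).

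| f | Rate per 100 | Power | N for 80% |
|---|---|---|---|
| 0 | 14.00 | 80.0% | 4667 |
| 1.5% | 13.79 | 79.4% | 4739 |
| 5% | 13.30 | 78.0% | 4913 |
| 8% | 12.88 | 76.7% | 5073 |

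*Case B: 14 per 100 was already DAD-only.* Power stays at the planned 80%. Adding ambulatory records would raise the rate to 14 / (1 − f):

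| f | Rate per 100 | Power |
|---|---|---|
| 1.5% | 14.21 | 80.6% |
| 5% | 14.74 | 81.9% |
| 8% | 15.22 | 83.1% |

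Section 4.8 attributes the rate to the team's administrative dataset and to Appendix VII, which is not in the supplied text. The two cases cannot be told apart.

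**The case against.** **The key premise is inferred.** No section says what DAD holds, or how often angioplasty or stenting was done as a day case. This stands, and the point is therefore conditional. A reader might go further and conclude that day-case procedures are definitely missed, or that the same procedure enters the cost outcome but not the clinical one. Section 12 mentions day surgery without mentioning angioplasty, so neither conclusion is established.

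**Section 4.6 is broader than DAD.** It describes primary-outcome sources in general terms and includes physician claims, and the header in 6.1 is already not exhaustive because death comes from elsewhere. But where 6.1 uses another source it names it, and it names none for revascularization. The general list does not fill the gap.

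**Inpatient-only is a usable definition.** Section 4.3 introduces these outcomes by speaking of hospitalization for complications, so a narrower operational rule, applied alike to all arms, could be defended. That is fair, but the narrowing should then be stated in 4.3.

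**The treatment effect is not biased.** Participants are individually randomized, all arms use the same provincial databases, and no mechanism for unequal loss is apparent. This stands. Reading the gap as a biased rate ratio would go beyond the documents.

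**It is late to change.** Follow-up ended in March 2021, and the introduction to the later SAP reports trial findings. That SAP covers beliefs, self-efficacy and adherence, and does not use revascularization. This stands and shapes the fix.

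**Conclusion.** The mismatch between sections 4.3 and 6.1 is real: the component is defined for any setting, and the only event source named for it is DAD. Its consequence depends on day-case procedures being absent from DAD, which is likely from the text but not stated there.

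If they are absent, the harm is fewer events, some loss of precision, and a revascularization component that is under-counted by its full day-case share. For the composite the loss is modest: about 0.6 to 3.3 power points (80% falling to 79.4% or 76.7%) on the assumed 1.5% to 8% of events missed, and only if the planning rate covered all settings. If that rate was discharge-only, nothing is lost against plan. A reader might infer that the trial was underpowered; the documents do not support this, since the stated sample size is reproduced exactly and the share missed is unknown.

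**What to change.** In section 6.1:

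1. Ascertain coronary revascularization from DAD or NACRS, using the same four CCI codes in both.
2. Count a procedure once when both databases carry it with the same procedure date (not admission date).
3. Name the event source for each component, with Vital Statistics for death, so that the header sentence no longer reads as DAD for everything.

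Because results are already reported, present the re-run as a sensitivity analysis beside the DAD-only count, for the composite and for the revascularization component, and do not replace the primary result. If it is not run, amend section 4.3 to say that only inpatient revascularization was counted.

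The cost is one extra query and a de-duplication step on a database that section 8 already lists for linkage. It depends on the NACRS extract carrying CCI procedure codes, which the documents do not confirm. The wording-only alternative costs one sentence.
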